4.4. End of Study Definition

For each part of the study, participants are considered to have completed the study if they complete the final visit on Day 181 (Month 6), six months after the study vaccination on Day 1.

The study will be considered ended at the completion of the last visit of the last participant in the Phase 2 Extension part of the study or the last scheduled procedure as shown in the SoE ([Table 3](#)) for the last participant in the Phase 2 Extension part of the study.

5. STUDY POPULATION

Prospective approval of protocol deviations to recruitment and enrollment criteria, also known as protocol waivers or exemptions, is not permitted.

5.1. Phase 1/2

5.1.1. Inclusion Criteria

Each participant must meet all of the following criteria at the Screening Visit and at Day 1, unless noted otherwise, to be enrolled in this study:

1. Is an adult, \geq 18 years of age at the time of consent (Screening Visit), who is in good health, in the opinion of the Investigator, based on review of medical history and physical examination performed at screening.
2. Understands and is willing and physically able to comply with protocol-mandated follow-up, including all procedures, in the opinion of the Investigator.
3. Has provided written informed consent for participation in this study, including all evaluations and procedures as specified in this protocol.
4. Has a body mass index (BMI) of 18 kg/m² to 35 kg/m² (inclusive) at the Screening Visit.
5. If female and is not of childbearing potential, may be enrolled in the study. The definition of a female of childbearing potential is provided in Appendix 2 ([Section 11.2](#)). A follicle-stimulating hormone (FSH) level may be measured at the discretion of the Investigator to confirm postmenopausal status.
6. If female and of childbearing potential, meets all of the following criteria to be enrolled in the study:
 - Has a negative pregnancy test at the Screening Visit and on the day of vaccination (Day 1).
 - Has practiced adequate contraception ([Section 11.2](#)) or has abstained from all activities that could result in pregnancy for at least 28 days prior to Day 1. Adequate female contraception is defined as consistent and correct use of an FDA-approved contraceptive method in accordance with the product label.
 - Has agreed to continue adequate contraception through 3 months following vaccine administration.
 - Is not currently breastfeeding.

5.1.2. Exclusion Criteria

Participant meeting any of the following criteria at the Screening Visit or at Day 1, unless noted otherwise, will be excluded from the study:

1. Has had significant exposure to someone with laboratory-confirmed SARS-CoV-2 infection, COVID-19, or ILI in the past 14 days prior to the Screening Visit, as defined by the CDC as close contact with someone who has COVID-19 ([CDC 2021a](#)).
2. Has a positive SARS-CoV-2 RT-PCR or antigen test in the past 10 days prior to the Screening Visit.
 - a. A participant who has a positive SARS-CoV-2 serological test in the past 10 days prior to the Screening Visit but is otherwise asymptomatic and does not have a positive SARS-CoV-2 RT-PCR or antigen test at the Screening Visit may still be enrolled if they meet the study eligibility criteria.
 - b. A participant who has a positive SARS-CoV-2 RT-PCR or antigen test in the past 10 days prior to the Screening Visit may be enrolled 10 days after symptom onset or 10 days after the date of the first positive SARS-CoV-2 RT-PCR test without repeat testing, provided the participant is asymptomatic and meets the study eligibility criteria as well as the CDC recommendation for duration of isolation and precautions ([CDC 2021b](#)).
 - c. Additionally, a participant who meets all study eligibility criteria (note exclusion criterion No. 4) at the Screening Visit but later tests positive for SARS-CoV-2 at Visit 1 will continue participation in the study.
3. Has clinical screening laboratory values (white blood cell [WBC] count, hemoglobin, platelets, alanine aminotransferase [ALT], aspartate aminotransferase [AST], creatinine, alkaline phosphatase, and total bilirubin) > Grade 1.
4. Is acutely ill or febrile (body temperature $\geq 38.0^{\circ}\text{C}/100.4^{\circ}\text{F}$) 72 hours prior to or at the Screening Visit or Day 1. Participants meeting this criterion may be rescheduled within the 28-day screening window and will retain their initially assigned participant number.
5. Has a pre-existing medical condition that is not stable, at the discretion of the Investigator. A stable medical condition is defined as disease not requiring significant change in therapy or hospitalization for worsening disease during the 2 months before enrollment. Participants may be rescreened if they are not medically stable at the Screening Visit. Medical conditions include (but are not limited to) the following:
 - a. Uncontrolled hypertension or systolic blood pressure (BP) > 150 mm Hg or diastolic BP > 90 mm Hg at the Screening Visit.

- b. Congestive heart failure.
- c. Unstable angina or exacerbation of coronary artery disease within 6 months before the day of vaccination (Day 1) requiring cardiac intervention or new cardiac medications to control symptoms.
- d. Diabetes requiring the use of medicine (injectable or oral) or not controlled with diet.
- e. Chronic obstructive pulmonary disease, asthma requiring daily use of a bronchodilator or inhaled/systemic corticosteroids, or other chronic lung diseases such as pulmonary fibrosis.
- 6. Has a medical, psychiatric, or occupational condition that may pose additional risk as a result of participation or that could interfere with safety assessments or interpretation of results according to the Investigator's judgment.
- 7. Has a current or previous diagnosis of immunocompromising condition, immune-mediated disease, or other immunosuppressive condition.
- 8. Has received systemic immunosuppressants or immune-modifying drugs for > 14 days in total within 6 months prior to Screening Visit (for corticosteroids \geq 10 mg/day of prednisone or equivalent) or is anticipating the need for immunosuppressive treatment at any time during participation in the study.
- 9. Has a history of anaphylaxis, urticaria, or other significant AR requiring medical intervention after receipt of a vaccine or any of the components contained in the IP.
- 10. Has a history of coagulopathy or bleeding disorder considered a contraindication to IM injection or phlebotomy.
- 11. Has received or plans to receive any licensed vaccine \leq 28 days prior to the IP injection (Day 1) or plans to receive a licensed vaccine within 28 days after the IP injection, with the exception of vaccines authorized or approved for the prevention of COVID-19 (regardless of type of vaccine) that become available to participants during the study. Efforts should be made to space study vaccination and COVID-19 vaccination by at least 7 and preferably 14 days, but COVID-19 vaccination should not be delayed.
- 12. Has received a seasonal influenza vaccine or any other investigational influenza vaccine after 01 Jan 2021.
- 13. Has received systemic immunoglobulins or blood products within 3 months prior to the Screening Visit or plans to receive them during the study.
- 14. Has a diagnosis of malignancy within the previous 10 years (excluding nonmelanoma skin cancer).

15. Has donated ≥ 450 mL of blood products within 28 days prior to the Screening Visit or plans to donate blood products during the study.
16. Has participated in an interventional clinical study within 28 days prior to the Screening Visit based on the medical history interview or plans to do so while participating in this study.
17. Is an immediate family member or household member of study personnel, study site staff, or Sponsor personnel.

5.2. Phase 2 Northern Hemisphere and Phase 2 Extension

5.2.1. Inclusion Criteria

Each participant must meet all of the following criteria at the Screening Visit and at Day 1, unless noted otherwise, to be enrolled in this study:

1. Is an adult, ≥ 18 years of age at the time of consent (Screening Visit), who in the opinion of the Investigator, is medically stable based on review of medical history and physical examination performed at screening. Medically stable is defined as disease not requiring significant change in therapy or hospitalization for worsening disease during the 3 months before enrollment. Participants may be rescreened if they are not medically stable at the Screening Visit.
2. Understands and is willing and physically able to comply with protocol-mandated follow-up, including all procedures, in the opinion of the Investigator.
3. Has provided written informed consent for participation in this study, including all evaluations and procedures as specified in this protocol.
4. If female and is not of childbearing potential, may be enrolled in the study. The definition of a female of childbearing potential is provided in Appendix 2 ([Section 11.2](#)). An FSH level may be measured at the discretion of the Investigator to confirm postmenopausal status.
5. If female and of childbearing potential, meets all of the following criteria to be enrolled in the study:
 - Has a negative pregnancy test at the Screening Visit and on the day of vaccination (Day 1).
 - Has practiced adequate contraception ([Section 11.2](#)) or has abstained from all activities that could result in pregnancy for at least 28 days prior to Day 1.

- Has agreed to continue adequate contraception through 3 months following vaccine administration. Adequate female contraception is defined as consistent and correct use of an FDA-approved contraceptive method in accordance with the product label.
- Is not currently breastfeeding.

5.2.2. Phase 2 Northern Hemisphere Exclusion Criteria

Participant meeting any of the following criteria at the Screening Visit or at Day 1, unless noted otherwise, will be excluded from the study:

1. Has had close contact to someone with SARS-CoV-2 infection or COVID-19 as defined by the CDC ([CDC 2021a](#)) in the past 14 days prior to the Screening Visit, unless the participant has been fully vaccinated for COVID-19.
2. Is acutely ill or febrile (body temperature $\geq 38.0^{\circ}\text{C}/100.4^{\circ}\text{F}$) 72 hours prior to or at the Screening Visit or Day 1. Participants meeting this criterion may be rescheduled within the 28-day screening window and will retain their initially assigned participant number.
3. Has a medical, psychiatric, occupational condition, or history of substance abuse that may pose additional risk as a result of participation or that could interfere with safety assessments or interpretation of results according to the Investigator's judgment.
4. Has a current or previous diagnosis of immunocompromising/immunosuppressive condition, immune-mediated disease requiring immune-modifying therapy, asplenia, recurrent severe infections (human immunodeficiency virus [HIV]-positive participants on antiretroviral therapy with cluster of differentiation [CD] 4 count ≥ 350 cells/mm³ and HIV-RNA ≤ 500 copies/mL within the past 12 months are permitted).
5. Has received systemic immunosuppressants or immune-modifying drugs for > 14 days in total within 6 months prior to the Screening Visit (for corticosteroids ≥ 10 mg/day of prednisone or equivalent) or is anticipating the need for systemic immunosuppressive treatment at any time during participation in the study.
6. Has a history of anaphylaxis, urticaria, or other significant AR requiring medical intervention after receipt of a vaccine or any of the components contained in the mRNA-1010 or the comparator vaccine, which is an egg-based influenza vaccine.
7. Has coagulopathy or bleeding disorder considered a contraindication to IM injection or phlebotomy.
8. Has received or plans to receive any licensed vaccine ≤ 28 days prior to the IP injection (Day 1) or plans to receive a licensed vaccine within 28 days after the IP vaccine injection, with the exception of vaccines authorized or approved for the prevention of

COVID-19 (regardless of type of vaccine) that become available to participants during the study. Efforts should be made to space study vaccination and COVID-19 vaccination by at least 7 and preferably 14 days, but COVID-19 vaccination should not be delayed.

9. Has received a seasonal influenza vaccine or any other investigational influenza vaccine within 6 months prior to the Screening Visit.
10. Had tested positive for influenza by CDC-recommended testing methods ([CDC 2020c](#)) within 6 months prior to the Screening Visit.
11. Has received systemic immunoglobulins or blood products within 3 months prior to the Screening Visit or plans to receive them during the study.
12. Has donated ≥ 450 mL of blood products within 28 days prior to the Screening Visit or plans to donate blood products during the study.
13. Has participated in an interventional clinical study within 28 days prior to the Screening Visit based on the medical history interview or plans to do so while participating in this study.
14. Is an immediate family member or household member of study personnel, study site staff, or Sponsor personnel.

5.2.3. Phase 2 Extension Exclusion Criteria

Participant meeting any of the following criteria at the Screening Visit or at Day 1, unless noted otherwise, will be excluded from the study:

1. Has had close contact to someone with SARS-CoV-2 infection or COVID-19 as defined by the CDC in the past 10 days prior to the Screening Visit.
2. Is acutely ill or febrile (body temperature $\geq 38.0^{\circ}\text{C}/100.4^{\circ}\text{F}$) 72 hours prior to or at the Screening Visit or Day 1. Participants meeting this criterion may be rescheduled within the 28-day screening window and will retain their initially assigned participant number.
3. Has a medical, psychiatric, occupational condition, or history of substance abuse that may pose additional risk as a result of participation or that could interfere with safety assessments or interpretation of results according to the Investigator's judgment.
4. Has a current or previous diagnosis of immunocompromising/immunosuppressive condition, immune-mediated disease requiring immune-modifying therapy, asplenia, recurrent severe infections (HIV-positive participants on antiretroviral therapy with CD 4 count ≥ 350 cells/mm³ and HIV-RNA ≤ 500 copies/mL within the past 365 days are permitted).

5. Has received systemic immunosuppressants or immune-modifying drugs for > 14 days in total within 180 days prior to Screening Visit (for corticosteroids \geq 10 mg/day of prednisone or equivalent) or is anticipating the need for systemic immunosuppressive treatment at any time during participation in the study.
6. Has a history of anaphylaxis, urticaria, or other significant AR requiring medical intervention after receipt of a vaccine or any of the components contained in the mRNA-1010 or the comparator vaccine, which is an egg-based influenza vaccine.
7. Has coagulopathy or bleeding disorder considered a contraindication to IM injection or phlebotomy.
8. Has received or plans to receive any licensed vaccine \leq 28 days prior to the IP injection (Day 1) or plans to receive a licensed vaccine within 28 days after the IP injection, with the exception of vaccines authorized or approved for the prevention of COVID-19 (regardless of type of vaccine) that become available to participants during the study. Efforts should be made to space study vaccination and COVID-19 vaccination by at least 7 and preferably 14 days, but COVID-19 vaccination should not be delayed.
9. Has received a seasonal influenza vaccine or any other investigational influenza vaccine within 180 days prior to the randomization visit.
10. Had tested positive for influenza by CDC-recommended testing methods within 180 days prior to the Screening Visit.
11. Has received systemic immunoglobulins or blood products within 90 days prior to the Screening Visit or plans to receive them during the study.
12. Has donated \geq 450 mL of blood products within 28 days prior to the Screening Visit or plans to donate blood products during the study.
13. Has participated in an interventional clinical study within 28 days prior to the Screening Visit based on the medical history interview or plans to do so while participating in this study.
14. Is an immediate family member or household member of study personnel, study site staff, or Sponsor personnel.

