Similarly, safety results from Phase 1 studies conducted by the Sponsor on 2 mRNA vaccines containing the HA glycoproteins from the H10N8 and H7N9 avian influenza viruses were well tolerated, although the Sponsor's LNP/mRNA platform has since been updated (eg, SM-102 is used in mRNA-1010 and mRNA-1273; [Feldman et al 2019](#)).

There have been very rare reports of myocarditis and pericarditis occurring after vaccination with COVID-19 mRNA vaccines. The majority of the cases have been reported in young males shortly after the second dose of the vaccine. These are typically mild cases and individuals tend to recover

within a short time following standard treatment and rest. Investigators and study participants should be alert to the signs and symptoms of myocarditis and pericarditis ([Gargano et al 2021](#)).

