Immunizations for the Phase 1/2 part of the study are planned during the NH summer and all participants will be recommended to receive a licensed 2021-2022 NH seasonal influenza vaccine during their participation in the study after completion of the Day 29 Visit. Immunizations for the Phase 2 NH part of the study are planned during the NH influenza season. Immunizations for the Phase 2 Extension part are planned during the NH spring.

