Section 2.3.2 (Risks From Study Participation and Their Mitigation)	
Added description of myocarditis and pericarditis following COVID-19 mRNA vaccines.	
To add information on very rare reports of myocarditis and pericarditis after vaccination with COVID-19 mRNA vaccines.
Section 4.1 (General Design) and Section 9.6 (Study Analyses)	
Clarified that the Phase 2 NH part will also assess reactogenicity.	
Revised for consistency of presentation.
Section 8.4.3 (Solicited Adverse Reactions)	
Clarified documentation of solicited adverse reaction collection.	
Revised for consistency of documentation.
Section 8.4.7 (Adverse Events of Special Interest)	
Added information on myocarditis/pericarditis events.	
To provide guidance to the Investigators regarding reporting myocarditis and pericarditis for this study population.
Section 10 (References)	
Updated reference list.	
To support the text added to the protocol for myocarditis and pericarditis.
Section 11.4.(APPENDIX 4: CDC Working Case Definition of Pericarditis, Myocarditis, and Myopericarditis Occurring After Receipt of COVID-19 mRNA Vaccines)	
Added CDC case definitions for myocarditis and pericarditis.Added description of independent CEAC as footnote to the table.	
To provide guidance to the Investigators regarding assessing and reporting myocarditis and pericarditis for this study population.To add mechanism for review of suspected cases of myocarditis and pericarditis.

Abbreviations: AESI = adverse event of special interest; CDC = Centers for Disease Control and Prevention; CEAC = Cardiac Event Adjudication Committee COVID-19 = coronavirus disease 2019; mRNA = messenger RNA; NH = Northern Hemisphere.

Amendment 3, 21 Oct 2021

Main Rationale for the Amendment:

The purpose of this amendment is to update the Phase 2 NH part of the study to test 3 dose levels of mRNA-1010 (25, 50, and 100 µg total mRNA; Vaccination Groups 1 to 3).

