IST	internal safety team
LLOQ	lower limit of quantification
MAAE	medically attended adverse event
max	maximum
MedDRA	Medical Dictionary for Regulatory Activities
min	minimum
MN	microneutralization
mRNA	messenger ribonucleic acid
NH	Northern Hemisphere

Abbreviation	Definition
NP	nasopharyngeal
PP	per-protocol
PT	preferred term
RT-PCR	reverse transcriptase polymerase chain reaction
SAE	serious adverse event
SAP	statistical analysis plan
SAS	Statistical Analysis System
SD	standard deviation
SoE	schedule of events
SOC	system organ class
TEAE	treatment-emergent adverse event
ULOQ	upper limit of quantification
WHO	World Health Organization
WHODrug Global	World Health Organization drug dictionary

1 Introduction

This statistical analysis plan (SAP), which describes the planned analyses for Study mRNA-1010-P101, is based on the most recent approved clinical study protocol (CSP), Amendment 4, dated 03-Feb-2022, and the most recent approved electronic case report form (eCRF), dated 01-Mar-2022.

In addition to the information presented in the statistical analysis plan section of the protocol (Section 9), which provides the principal features of analyses for this study, this SAP provides statistical analysis details/data derivations. It also documents modifications or additions to the analysis plan that are not “principal” in nature and result from information that was not available at the time of protocol finalization.

Study mRNA-1010-P101 is a Phase 1/2, randomized, stratified, observer-blind, dose-ranging study to evaluate the safety, reactogenicity, and immunogenicity of messenger ribonucleic acid (mRNA)-1010 seasonal influenza vaccine in healthy adults 18 years and older. Study design and analyses for Phase 1/2, and Phase 2 Northern Hemisphere, and Phase 2 Extension parts of the study will be described separately in the SAP, unless otherwise specified.

PPD Biostatistics and Programming team, designee of Moderna Biostatistics and Programming department, will perform the statistical analysis of the safety, reactogenicity, and immunogenicity data; Statistical Analysis System (SAS) Version 9.4 or higher will be used to generate all statistical outputs (tables, figures, listings, and datasets). The SAP will be finalized and approved prior to the primary analysis clinical database lock and treatment unblinding for the study. If the methods in this SAP differ from the methods described in the protocol, the SAP will prevail.

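### The Phase 2 Extension criteria leave open re-entry by Phase 1/2 mRNA-1010 recipients, and neither the analysis sets nor the planned tables would identify them

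*Protocol*

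**What the plan says.** Protocol Section 5.2.3 lists 14 exclusions for the Phase 2 Extension. Two bear on a person who was in an earlier part:

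- No. 9 excludes a person who "Has received a seasonal influenza vaccine or any other investigational influenza vaccine within 180 days prior to the randomization visit".
- No. 13 excludes a person who "Has participated in an interventional clinical study within 28 days prior to the Screening Visit", or who plans to join one during this study.

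Neither these exclusions nor the inclusion criteria in Section 5.2.1 mention earlier receipt of mRNA-1010 or earlier randomisation in mRNA-1010-P101.

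Section 4.1 gives the timing: "Immunizations for the Phase 1/2 part of the study are planned during the NH summer", and "Immunizations for the Phase 2 Extension part are planned during the NH spring". It also recommends that Phase 1/2 participants take a licensed 2021-2022 influenza vaccine after their Day 29 Visit. The vaccines in the two parts share three of four HA components (A/Wisconsin/588/2019 H1N1, B/Washington/02/2019, B/Phuket/3073/2013). Only the H3N2 strain differs.

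Extension randomisation is stratified by age alone (Protocol Section 6.2.3), whereas Phase 2 NH also stratifies by previous-season vaccination (Section 6.2.2).

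**The concern.** The Extension is meant to describe what one low dose of mRNA-1010 does. A person given 50, 100 or 200 µg in Phase 1/2 would be on a second exposure to the product, with three antigens repeated. Two outputs are exposed.

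- **Reactogenicity.** Solicited reactions are tabulated by the Extension dose received. Nothing separates a second exposure from a first.
- **Seroconversion.** When baseline is at or above the threshold, the definition requires a 4-fold rise. A person whose titers are still raised from an earlier dose may be less likely to reach it. The SAP adjusts the Day 29 GMT model for baseline titer (Section 6.4.3.1) but gives the seroconversion difference an unadjusted Miettinen-Nurminen interval. Absolute seroconversion in each vaccine group is also a secondary endpoint.

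Later steps would not find such a person. The vaccine history in Protocol Section 6.5.2 covers seasonal influenza vaccine since September 2021 for the Extension, and other non-COVID vaccines only from 28 days before injection. The PP Set rules (Protocol Section 9.4 and Section 6.5.3; SAP Section 5.3) do not mention earlier mRNA-1010, and the Safety Set (SAP Section 5.4) assigns people by the dose received in that part.

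**Working it through.** **1. The plan's own Extension figure.** Protocol Section 9.3 and SAP Section 4.3.3 give about 92% and 99% for seeing at least one participant with an AE among 50. The formula is 1 − (1 − p)^n.
- p = 5%: 1 − 0.95^50 = 92.3%.
- p = 10%: 1 − 0.90^50 = 99.5%.

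Both agree with the plan. They describe 50 first exposures per dose group only if there are no re-entrants.

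**2. When Phase 1/2 recipients become eligible.** The Phase 1/2 interim analysis follows all participants' Day 29 Visits (Protocol Section 9.6), and its results are the rationale for "Amendment 3, 21 Oct 2021", used here only as a date. The Day 29 window is ±2 days, so the earliest such visit is Day 27, which is 26 days after injection.
- Latest injection: 21 Oct 2021 − 26 days = 25 Sep 2021.
- Exclusion 9: 25 Sep 2021 + 180 days = 24 Mar 2022.
- Exclusion 13, if Phase 1/2 counts as an interventional study and the last visit is at the end of its window (Day 195): 25 Sep 2021 + 194 days = 7 Apr 2022; + 28 days = 5 May 2022.
- An injection on 22 Jul 2021, with Day 181 on schedule, clears on 18 Jan 2022 (exclusion 9) and 15 Feb 2022 (exclusion 13).

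The Extension was added by "Amendment 4, dated 03-Feb-2022", so its spring is 2022. The documents do not define spring; on a March-to-May reading, even the latest date falls inside it.

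**3. Effect of the licensed-vaccine recommendation.** A licensed dose restarts the 180 days:
- 1 Oct 2021 → 30 Mar 2022
- 31 Oct 2021 → 29 Apr 2022
- 30 Nov 2021 → 29 May 2022

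The opening narrows for those who followed the advice but does not close.

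**4. Pool.** Phase 1/2 has 3 × 45 = 135 planned mRNA-1010 recipients; the Extension has 200 places. The documents give no re-entry count.

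**5. Seroconversion within an arm (all rates assumed).** With share f of re-entrants, the arm rate is (1 − f) × p + f × q, so the fall is f × (p − q). Take p = 60% in others and q = 30%, 20% or 10% in re-entrants.

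| Share f | Re-entrants per 50 | Fall, q = 30% | Fall, q = 20% | Fall, q = 10% |
|---|---|---|---|---|
| 5% | 2.5 | 1.5 points | 2 points | 2.5 points |
| 10% | 5 | 3 points | 4 points | 5 points |
| 20% | 10 | 6 points | 8 points | 10 points |

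Five per arm means 20 across four arms, or 20/135 = 15% of Phase 1/2 mRNA-1010 recipients. Ten per arm means 40/135 = 30%.

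**6. Difference versus comparator.** Re-entrants would be randomised 1:1:1:1. If D is the group difference in others and D′ that in re-entrants, the expected observed difference is (1 − f) × D + f × D′.
- D′ = D: no change.
- D = 20 points, D′ = 0, f = 10%: 0.9 × 20 = 18 points.
- Chance imbalance, for example 7 re-entrants in one arm and 3 in the comparator with p = 60% and q = 20%: (7 − 3)/50 × 40 = 3.2 points.

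**7. First-exposure safety data.** The chance of seeing at least one AE of 5% incidence among first exposures in a group is:
- f = 5% (47.5 people): 91.3%
- f = 10% (45 people): 90.1%
- f = 20% (40 people): 87.1%

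**The case against.** The strongest reply is that re-entry is hypothetical. The planned total of 880 is exactly 180 + 500 + 200, which presumes distinct people; the study is described as giving each participant a single dose; and no text provides for a completer to join again. This stands as evidence of intent. It is not an eligibility rule, and a site applying Section 5.2.3 as written would have no ground to refuse such a person.

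The licensed-vaccine advice also stands as a real barrier for those who followed it. Randomisation answers much of the worry about the comparison, since expected dilution falls on all four arms, comparator included. It does not protect absolute seroconversion rates or the labelling of reactogenicity. The study tests no hypothesis, which lowers the stakes of a shift of a few points.

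A reader might infer two stronger things. One is that re-entrants would contaminate an otherwise naive population. The documents do not support that: seasonal vaccine more than 180 days earlier and COVID-19 vaccination are both allowed, the seroconversion definition has a branch for people with detectable baseline titers, and the GMT model adjusts for baseline. The other is a specific myocarditis risk, because Protocol Section 2.3.2 says "The majority of the cases have been reported in young males shortly after the second dose of the vaccine". That sentence concerns COVID-19 mRNA vaccines, and the documents hold no second-dose data for mRNA-1010.

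**Conclusion.** The gap in the eligibility text is real. Exclusions 9 and 13 delay Phase 1/2 mRNA-1010 recipients but do not keep them out of a spring 2022 Extension, and the recorded vaccine history, strata, analysis sets and tables would not identify them. No document shows that anyone re-entered. The number is unknown and may be small.

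The firm consequence is that any re-entrant's solicited reactions would be reported as single-dose data although they follow a second exposure; the documents do not say in which direction these would differ. Lower absolute seroconversion is plausible in every arm, by 1.5 to 10 points over the assumed ranges. It would be wrong to read this as a bias in the comparison with the active comparator: that difference moves only if the group effect differs in re-entrants or by chance imbalance. The re-entry shares and response rates are assumptions, and the dates rest on interim results existing by 21 Oct 2021. The point is worth correcting because the correction is cheap.

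**What to change.** Add an Extension exclusion for prior randomisation in any other part of mRNA-1010-P101. Wording by randomisation rather than by receipt of mRNA-1010 matters: under Protocol Section 9.6, sites and participants stay blinded until after final database lock, so a site may be unable to tell who had mRNA-1010 and who had placebo. The same wording also covers Phase 2 NH.

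If enrolment has begun:
- Cross-check Extension participants against the other parts.
- State in the SAP, before any Extension unblinding including the Day 29 interim analysis, that re-entrants are excluded from the PP Set.
- Keep them in the Safety Set but show their solicited and unsolicited safety data separately.

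The cost is one criterion and one check at screening. The downside is a slightly smaller recruitment pool at sites that ran earlier parts, including the loss of former placebo recipients. Provided 50 per group are still enrolled, the plan's 92% and 99% figures are unchanged and then refer to first exposures in each mRNA-1010 group.
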